
• In compliance with ICH requirements, the protocol mentions that all results will be presented in an integrated report at the end of the study.• Following re-development and re-validation of the anti-PD ELISA, a new cut-off was defined.• Reference to the GSK Biologicals' Laval laboratory was removed, as this laboratory will not be used in the study. In addition, this laboratory is no longer part of GSK Biologicals' laboratories.• Internal assay qualification procedures were revised and it was decided that the level of characterisation of the ELISA assays can be minimal (set-up level) for this study as immunogenicity data are descriptive. In consequence, the assays will be standardized but not qualified as stated in the original version. This change will not impact the validity of the results.• A tertiary endpoint was added as the presence of viral pathogens in sputum will be examined as part of microbiome analysis.• In order to see early effects of the vaccine on the microbiome, analysis on fresh sputum samples (culture results) will be done on all available data up to the data lock point of the interim analysis.• In order to have a first look whether or not the investigational vaccine has an impact on AECOPD, AECOPD analyses will be done up to the data lock point of the interim analysis.• Wording was added to clarify process for collection of sputum H. influenzae sweeps.• Wording was updated in order to be aligned with the Statistical Ananlysis Plan.• In addition, minor edits in other sections were made for clarification purposes.	

Protocol Amendment 3 Investigator Agreement

I agree:

- To conduct the study in compliance with this protocol, any future protocol amendments or protocol administrative changes, with the terms of the clinical trial agreement and with any other study conduct procedures and/or study conduct documents provided by GlaxoSmithKline (GSK) Biologicals.
- To assume responsibility for the proper conduct of the study at this site.
- That I am aware of, and will comply with, 'Good Clinical Practice' (GCP) and all applicable regulatory requirements.
- To ensure that all persons assisting me with the study are adequately informed about the GSK Biologicals' investigational vaccine and other study-related duties and functions as described in the protocol.

GSK Biologicals Central Back-up Study Contact for Reporting SAEs: refer to protocol Section [9.4.3.1](#).

5. GSK Biologicals' Central Safety Physician On-Call Contact information for Emergency unblinding

GSK Biologicals' Central Safety Physician and Back-up Phone contact: refer to protocol Section [9.8](#).

SYNOPSIS

Detailed Title	A Phase II, randomised, observer-blind, placebo-controlled, multi-centre study to evaluate the safety, reactogenicity and immunogenicity of GSK Biologicals' investigational vaccine GSK2838504A, when administered intramuscularly according to a 0, 2 month schedule to COPD patients aged 40 to 80 years
Indication	Active immunisation to reduce the frequency of Non-typeable Haemophilus influenzae (NTHi)-associated moderate and severe acute exacerbations (AECOPD) in COPD patients with a previous history of AECOPD
Rationale for the study and study design	Rationale for the study The purpose of this Phase II study, in which the investigational NTHi vaccine will be administered for the first time to moderate and severe COPD patients (i.e. GOLD grade 2 and 3), is to assess the vaccine's safety, reactogenicity and immunogenicity in this population, and to evaluate in an exploratory manner whether an NTHi vaccine can reduce the frequency of moderate and severe AECOPD associated with NTHi. Placebo will be used as a control. Both the investigational NTHi vaccine and the placebo will be given on top of the standard of care.
	Rationale for the study design 
• Scheduled study visits, during which the effect of immunisation against NTHi will be evaluated, will take place at pre-defined timepoints. In addition, ad-hoc AECOPD-driven study visit(s) and/ or phone contact(s) will take place for each AECOPD occurring from first vaccination up to study conclusion. Besides evaluating the effect of vaccination against NTHi on AECOPD, the information obtained during these AECOPD-driven study contacts will help refining the case definition of AECOPD and of NTHi-associated AECOPD.• As the investigational vaccine will be administered for the first time to moderate and severe COPD patients, an internal Safety Review Committee (iSRC) will be appointed next to the existing project's Safety Review Team (SRT) and safety holding rules have been defined. 
Administration vaccine Dose 1 will follow a staggered design, starting with vaccination of GOLD 2 subjects only. Administration of vaccine Dose 1 to GOLD 3 subjects will depend on the favourable outcome of an iSRC evaluation of safety data up to at least day 6 after vaccination from

about 20 GOLD 2 subjects (*i.e.* approximately 10 subjects/group).

In addition, starting administration of **vaccine Dose 2** will for each GOLD grade depend on the favourable outcome of an iSRC evaluation of all available safety data.

Rationale for the use of placebo

There is currently no established vaccine with recognised efficacy in reducing the frequency of NTHi-associated AECOPD. Placebo will therefore be used as a control.

Objectives

Primary

- To describe the safety and reactogenicity of the investigational vaccine.

Secondary

- To describe the humoral and cellular immunogenicity of the investigational vaccine.

Tertiary

- To explore the impact of the investigational vaccine on AECOPD.
- To explore the impact of the investigational vaccine on NTHi presence in sputum.
- To explore the impact of the investigational vaccine on health-related quality of life (HRQOL).
- To explore the impact of the investigational vaccine on lung function.
- To explore the impact of the investigational NTHi vaccine on exercise capacity.
- To describe selected biomarkers in stable COPD and during AECOPD.
- To collect blood and sputum samples for assay development, for disease diagnostic purpose, for lung microbiome analysis and/ or for additional evaluation of the immune responses to the investigational vaccine and to other potential pathogens involved in AECOPD.

Study design

- **Experimental design:** Phase II randomised, observer-blind, placebo-controlled, multi-centre study with 2 parallel groups.
- **Duration of the study:** for each subject enrolled, the study will last approximately 16 months from Visit 1 up to study end:
 - **Epoch 001:** starting at Screening and ending at study conclusion.
- **Study groups:**
 - **Group 10-AS01E:** approximately 70 subjects receiving 2 doses of the investigational NTHi vaccine.
 - **Group Control:** approximately 70 subjects receiving 2 doses of placebo.

Synopsis Table 1 Study groups and epoch foreseen in the study

Study groups	Number of subjects	Age (Min/Max)	Epoch
			Epoch 001
10-AS01E	~70	40 - 80 years	X
Control	~70	40 - 80 years	X

- **Control:** placebo control.
- **Vaccination schedule:** 0, 2 months (*i.e.* at Visit 1 [Day 0] and Visit 4 [Day 60]).

Synopsis Table 2 Study groups and treatments foreseen in the study

Treatment name	Vaccine/ product name	Study groups	
		10-AS01E	Control
10µgAg/ AS01 _E	NTHi-10	X	
	AS01E		
Placebo	NaCl		X

- **Treatment allocation:** subjects will be minimised by:
 - Age (40 - 59 years or 60 - 80 years).
 - Number of moderate/ severe AECOPD in the previous year (< 2 or ≥ 2).
 - GOLD grade (GOLD 2 or GOLD 3).

All factors will have equal weight in the minimisation algorithm.

- **Blinding:** observer-blind.

Synopsis Table 3 Blinding of study epochs

Study Epochs	Blinding
Epoch 001	observer-blind

- **Sampling schedule:**

- **Blood samples for safety assessment** (haematology/biochemistry parameters) will be collected from all subjects at the Screening Visit (pre-Day 0), Visit 1 (Day 0), Visit 2 (Day 7), Visit 3 (Day 30), Visit 4 (Day 60), Visit 5 (Day 67), Visit 6 (Day 90), Visit 8 (Day 270) and at Visit 10 (Day 450).
- **Blood samples for assessment of humoral immunogenicity** will be collected from all subjects at Visit 1 (Day 0), Visit 3 (Day 30), Visit 4 (Day 60), Visit 6 (Day 90), Visit 8 (Day 270) and at Visit 10 (Day 450).
- **Blood samples for assessment of cell-mediated immunogenicity (CMI)** will be collected from all subjects in the CMI sub-cohort at Visit 1 (Day 0), Visit 6 (Day 90), Visit 8 (Day 270) and at Visit 10 (Day 450).
- **Blood samples for biomarkers** will be collected from all subjects at Visit 1 (Day 0), Visit 10 (Day 450) and at each AECOPD visit from first vaccination to study conclusion.
- **Blood samples for assessment of haematology** parameters will be collected at each AECOPD visit.
- **Sputum samples** will be collected from all subjects at the Screening Visit (pre-Day 0), Visit 6 (Day 90), Visit 7 (Day 180), Visit 8 (Day 270), Visit 9 (Day 360), Visit 10 (Day 450) and at each AECOPD visit from first vaccination to study conclusion.

- **COPD symptoms:** All subjects will be asked to record COPD symptoms in their electronic Diary Card:
 - Daily in the morning throughout the study (including during AECOPD): **morning symptoms**.
 - Daily at bedtime throughout the study (including during AECOPD): **EXACT-PRO**.

- **HRQOL assessments:**
 - All subjects will be asked to complete the **COPD assessment test (CAT)** at the Screening Visit (pre-Day 0), Visit 8 (Day 270), Visit 10 (Day 450) and at each AECOPD visit from first vaccination to study conclusion.
 - All subjects will be asked to complete **St. George's Respiratory Questionnaire for COPD patients (SGRQ-C)** at the Screening Visit (pre-Day 0), Visit 8 (Day 270) and at Visit 10 (Day 450).
 - All subjects will be asked to complete the **Medical Research Council Dyspnoea (mMRC) scale** at the Screening Visit (pre-Day 0), Visit 8 (Day 270), Visit 10 (Day 450) and at each AECOPD visit from first vaccination to study conclusion.
- **Pre- and post-bronchodilator spirometry assessments** will be done for all subjects at the Screening Visit (pre-Day 0), Visit 8 (Day 270) and at Visit 10 (Day 450).
- **Exercise capacity:** all subjects will be asked to perform the 6-Minute Walk Test (6MWT) at the Screening Visit (pre-Day 0) and at Visit 10 (Day 450).
- **Type of study:** self-contained.
- **Data collection:** electronic Case Report Form (eCRF), electronic Diary Cards and SITEpro tablets.
- **Safety monitoring:** safety evaluations by the SRT (blinded) and by an iSRC (unblinded) will be performed.

Number of subjects The targeted sample size is ~70 subjects/ group (*i.e.* 140 subjects in total).

Endpoints (Amended 15 April 2016)

Primary

- Occurrence of each solicited local adverse event (AE), during the 7-day follow-up period (*i.e.* day 0 - 6) following each vaccination, in all subjects.
- Occurrence of each solicited general AE, during the 7-day follow-up period (*i.e.* day 0 - 6) following each vaccination, in all subjects.
- Occurrence of any unsolicited AE, during the 30-day follow-up period (*i.e.* day 0 - 29) following each vaccination, in all subjects.

- Occurrence of each haematological/ biochemical laboratory abnormality at Day 0, Day 7, Day 30, Day 60, Day 67, Day 90, Day 270 and Day 450, in all subjects.
- Occurrence of any potential immune-mediated disease (pIMD) from first vaccination up to study conclusion, in all subjects.
- Occurrence of any serious adverse event (SAE) from first vaccination up to study conclusion, in all subjects.

Secondary

- Anti-PD, anti-PE and anti-PilA total IgG antibody concentrations as measured by ELISA, at Day 0, Day 30, Day 60, Day 90, Day 270 and at Day 450, in all subjects.
- NTHi-specific cell-mediated immune responses as measured by flow cytometry intracellular cytokine staining (ICS) (frequency of specific CD4⁺/CD8⁺ T-cells expressing two or more markers, such as IL-2, IL-13, IL-17, IFN- γ , TNF- α and CD40L), at Day 0, Day 90, Day 270 and at Day 450, in a sub-cohort of subjects.

Tertiary

- Number of cases of NTHi-associated moderate and severe AECOPD, over a period starting 1 month post-Dose 2 and lasting for 1 year, in all subjects.
- Number of cases of NTHi-associated AECOPD (any severity), over a period starting 1 month post-Dose 2 and lasting for 1 year, in all subjects.
- Number of cases of moderate and severe AECOPD (any cause), over a period starting 1 month post-Dose 2 and lasting for 1 year, in all subjects.
- Number of cases of AECOPD (any cause, any severity), over a period starting 1 month post-Dose 2 and lasting for 1 year, in all subjects.
- Time to first AECOPD, in all subjects.
- Assessment of EXACT-PRO score, daily at bedtime throughout the study, in all subjects.
- NTHi presence in sputum, at Screening, Day 90, Day 180, Day 270, Day 360 and Day 450, and from first vaccination to study conclusion for each AECOPD, in all subjects.

- Assessment of *CAT* score, at Screening, Day 270 and Day 450, and from first vaccination to study conclusion for each AECOPD, in all subjects.
- Assessment of SGRQ-C score, at Screening, Day 270 and Day 450, in all subjects.
- Assessment of mMRC scale, at Screening, Day 270 and Day 450, and from first vaccination to study conclusion for each AECOPD, in all subjects.
- Occurrence of rescue medication use, over a period starting 1 month post-Dose 2 and lasting for 1 year, in all subjects.
- Occurrence of healthcare use for AECOPD, over a period starting 1 month post-Dose 2 and lasting for 1 year, in all subjects.
- Assessment of FEV₁% of predicted normal value at Screening, Day 270 and Day 450, in all subjects.
- Assessment of 6MWT score, at Screening and Day 450, in all subjects.
- Occurrence of selected biomarkers in a subset of blood samples, at Day 0 and Day 450, and from first vaccination to study conclusion for each AECOPD, in all subjects.
- *Presence of respiratory viral pathogens in sputum (including respiratory syncytial virus, parainfluenza virus, enterovirus/ rhinovirus, metapneumovirus, influenza virus, adenovirus, bocavirus and coronavirus) at Screening, Day 90, Day 180, Day 270, Visit Day 360 and Day 450 and at each AECOPD visit from first vaccination to study conclusion, in all subjects.*

TABLE OF CONTENTS

	PAGE
SPONSOR INFORMATION	7
SYNOPSIS	8
LIST OF ABBREVIATIONS	24
GLOSSARY OF TERMS	27
1. INTRODUCTION	32
1.1. Background	32
1.1.1. Chronic obstructive pulmonary disease and acute exacerbations	32
1.1.2. Current management of AECOPD	33
1.1.3. GSK Biologicals' investigational NTHi vaccine	33
1.2. Rationale for the study and study design	33
1.2.1. Rationale for the study	33
1.2.2. Rationale for the study design	34
1.2.2.1. Scheduled study visits and AECOPD-driven study contacts	34
1.2.2.2. Safety overview and staggered vaccination	34
1.2.3. Rationale for the use of placebo	35
1.3. Benefit: Risk assessment	35
1.3.1. Risk Assessment	35
1.3.2. Benefit Assessment	35
1.3.3. Overall Benefit : Risk Conclusion	35
2. OBJECTIVES	36
2.1. Primary objective	36
2.2. Secondary objective	36
2.3. Tertiary objectives	36
3. STUDY DESIGN OVERVIEW	37
4. AECOPD	40
4.1. Detection of AECOPD	40
4.1.1. Date of onset and end date of AECOPD	41
4.1.2. Guideline for assessing AECOPD that increase in severity	41
4.2. Treatment of AECOPD	41
4.2.1. Guidelines for treatment with antibiotics	41
4.2.2. Guidelines for treatment with systemic corticosteroids	41
4.3. Case definition NTHi-associated AECOPD	42
5. STUDY COHORT	42
5.1. Number of subjects	42
5.2. Inclusion criteria for enrolment	42
5.3. Exclusion criteria for enrolment	43
6. CONDUCT OF THE STUDY	45

6.1.	Regulatory and ethical considerations, including the informed consent process.....	45
6.2.	Subject identification and randomisation of treatment.....	46

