3. STUDY DESIGN OVERVIEW

Protocol waivers or exemptions are not allowed with the exception of immediate safety concerns. Therefore, adherence to the study design requirements, including those specified in the outline of study procedures (Section 6.5), are essential and required for study conduct.

Figure 1 Study design overview

Scr = Screening; **V** = Visit; **D** = Day; **random** = randomisation; **VACC** = vaccination; **BS(1)** = blood sample for safety; **BS(2)** = blood sample for humoral immunogenicity; **BS(3)** = blood sample for cell-mediated immunity (CMI); **BS(4)** = blood sample for biomarkers; **SP** = sputum sample

In addition to the scheduled study visits depicted above, *ad hoc* AECOPD-driven study visit(s) and/or phone contact(s) will take place for each AECOPD occurring from first vaccination up to study conclusion. An AECOPD visit will be scheduled as soon as possible after the onset of AECOPD symptoms (maximum 96 hours after and, if applicable, preferably before starting treatment with antibiotics). In addition, follow-up phone call(s) and/or visit(s) will take place to determine the end of the AECOPD. These contacts will take place at least every 2 weeks, until the AECOPD has resolved.

- **Experimental design:** Phase II randomised, observer-blind, placebo-controlled, multi-centre study with 2 parallel groups.
- **Duration of the study:** for each subject enrolled, the study will last approximately 16 months from Visit 1 up to study end:
 - **Epoch 001:** starting at Screening and ending at study conclusion.
- **Study groups:**
 - **Group 10-AS01E:** approximately 70 subjects receiving 2 doses of the investigational NTHi vaccine.
 - **Group Control:** approximately 70 subjects receiving 2 doses of placebo.

Table 3 Study groups and epoch foreseen in the study

Study groups	Number of subjects	Age (Min/Max)	Epoch
			Epoch 001
10-AS01E	~70	40 - 80 years	X
Control	~70	40 - 80 years	X

- **Control:** placebo control.
- **Vaccination schedule:** 0, 2 months (*i.e.* at Visit 1 [Day 0] and Visit 4 [Day 60]).

Table 4 Study groups and treatments foreseen in the study

Treatment name	Vaccine/ product name	Study groups	
		10-AS01E	Control
10µgAg/ AS01E	NTHI-10	X	
	AS01E		
Placebo	NaCl		X

- **Treatment allocation:** subjects will be minimised by:
 - Age (40 - 59 years or 60 - 80 years).
 - Number of moderate/ severe AECOPD in the previous year (< 2 or \geq 2).
 - GOLD grade (GOLD 2 or GOLD 3).

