6.2.2.2. Treatment allocation to the subject

The treatment numbers will be allocated by dose.

6.2.2.2.1. *Study group and treatment number allocation*

The target will be to enrol approximately 140 eligible subjects who will be randomly assigned to the 2 study groups in a (1:1) ratio (approximately 70 subjects in each group).

Allocation of a subject to a study group at the investigator site will be performed using a centralised randomisation system on the internet (SBIR). The randomisation algorithm will use a minimisation procedure accounting for age (40 - 59 years or 60 - 80 years), number of moderate/ severe AECOPD in the previous year (< 2 or \geq 2) and GOLD grade (GOLD 2 or GOLD 3). All factors will have equal weight in the minimisation algorithm.

At Visit 1, before administration of vaccine Dose 1 to eligible subjects who signed and dated the ICF at the Screening Visit, the dedicated site staff will access SBIR. Upon providing the subject's age category (40 - 59 years or 60 - 80 years), number of moderate/ severe AECOPD in the previous year and his/ her GOLD grade, the randomisation system will determine the study group and will provide the treatment number to be used for the first dose.

The number of each administered treatment must be recorded in the eCRF on the Vaccine Administration screen.

When SBIR is not available, refer to the SBIR user guide or the SPM for specific instructions.

6.2.2.2.2. *Treatment number allocation for subsequent doses*

For each dose subsequent to the first dose, the dedicated study staff will access SBIR. Upon providing the subject identification number, the system will provide a treatment number consistent with the allocated study group.

The number of each administered treatment must be recorded in the eCRF on the Vaccine Administration screen.

When SBIR is not available, refer to the SBIR user guide or the SPM for specific instructions.

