6.1.3. Analysis of impact of the investigational vaccine on AECOPD incidence

The analysis will be performed on the ATP cohort for efficacy. If the percentage of vaccinated subjects excluded from the ATP cohort for efficacy is more than 10%, a second analysis based on the TVC will be performed to complement the first analysis.

The following incidence rates will be computed over a period starting 1 month post-Dose 2 and lasting for 1 year, with 95%CI:

- NTHi-associated moderate and severe AECOPD. (See definition in section 7.1.4)
- NTHi-associated all-severity AECOPD.
- All-cause moderate and severe AECOPD.
- All-cause, all-severity AECOPD.

Vaccine efficacy (VE) for AECOPD events will be defined as:

$$VE (AECOPD) = 1 - R_{vaccine} / R_{control}$$

with:

- $R_{vaccine}$ = average yearly incidence rate of AECOPD events per subject in the group 10-AS01E.
- $R_{control}$ = average yearly incidence rate of AECOPD events per subject in the Control group.

In case the 95% CI of the VE cannot be estimated, *e.g.* when no event is observed in the group 10-AS01E (leading to a VE of 100%), then an exact procedure will be used to estimate a VE and its 95% CI. This exact procedure will be based on the number of subjects with event instead of on the average number of event per subject in each group.

Statistical Analysis Plan

Study alias & e-track number(s): NTHi-004 (200157)

VE in the prevention of NTHi-associated moderate and severe AECOPD and its 95% CI will be calculated.

VE in the prevention of NTHi-associated all-severity AECOPD, of all-cause moderate and severe AECOPD and of all-cause, all-severity AECOPD and their 95% CI will also be calculated.

The 95%CI of the incidence rate will be computed using a model which accounts for repeated events. The Generalised linear model assuming the Negative Binomial distribution for the response variable with logarithm as link function, and the logarithm of time for follow-up as an offset variable will be used. In addition, the following covariates (as per randomization) will be taken into account:

- country,
- number of moderate/severe exacerbations reported in the 12 months prior to enrolment,
- COPD status at enrolment (derived by GSK from the Visit 1 spirometry results)
- Age (below or equal to median/above median)

If the model does not converge, the Poisson distribution will be used instead of the Negative Binomial one.

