7.1.4. NTHi associated AECOPD

An NTHi associated to AECOPD is not yet well defined at the time of the SAP is written. Here is the first approach:

- An AECOPD for which NTHi was observed: Hi confirmed first by culture and then by PCR.

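### The vaccine-efficacy models for NTHi-associated AECOPD leave out Screening-sputum H. influenzae status, so a chance carriage imbalance can move the VE estimate; the effect is modest and is not a bias

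*Protocol*

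**What the plan says.** **Measurement.** Protocol Synopsis (Endpoints) and Section 11.3 list "NTHi presence in sputum, at Screening, Day 90, Day 180, Day 270, Day 360 and Day 450" among the tertiary endpoints. The sampling schedule says that sputum "will be collected from all subjects at the Screening Visit (pre-Day 0), Visit 6 (Day 90), Visit 7 (Day 180" and onward. Table 7 adds that sputum is taken only if the investigator considers it safe. Under Section 6.7.3, fresh-sputum culture results are entered in the eCRF.

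**Allocation.** Section 6.2.2.2: "The target will be to enrol approximately 140 eligible subjects who will be randomly assigned to the 2 study groups in a (1:1) ratio". "The randomisation algorithm will use a minimisation procedure accounting for age", exacerbation history "and GOLD grade (GOLD 2 or GOLD 3). All factors will have equal weight in the minimisation algorithm". No sputum result is in that list.

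**Model.** SAP Amendment 1, Section 6.1.3, specifies a negative binomial model with log link and log follow-up offset, falling back to Poisson if it does not converge. "In addition, the following covariates (as per randomization) will be taken into account": country, number of earlier moderate/severe exacerbations, COPD status and age. Country is there although allocation did not use it, so the list already goes beyond the minimisation factors.

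**Case definition.** SAP Section 7.1.4 says the definition is not yet settled and gives a first approach: "An AECOPD for which NTHi was observed: Hi confirmed first by culture and then by PCR". Protocol Section 4.3 leaves open presence, bacterial load or acquisition of a new strain.

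**Nearby provisions.**
- Protocol Section 11.10 tabulates sputum positivity by visit, pathogen and group.
- SAP Section 6.1.3 also models AECOPD with H. influenzae in culture that was absent at the previous visit.
- SAP Section 6.1.7.5 separates AECOPD by earlier H. influenzae findings.
- For antibodies, SAP Section 6.1.2 adjusts the GMC ratio for the pre-Dose 1 concentration.

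**The concern.** Under an any-presence definition, a subject who persistently carries H. influenzae can count as a case at an exacerbation of any cause. Carriage before vaccination is therefore a plausible strong predictor of the endpoint. It is planned to be measured before randomisation, so the vaccine cannot have affected it.

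With about 70 subjects per group and no balancing on carriage, the groups may differ on it by chance. An unadjusted estimate then carries that difference into the VE. NTHi-associated moderate and severe AECOPD is the first-listed tertiary endpoint and corresponds to the stated indication.

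Timing also matters. SAP Section 8.1 unblinds the project statistician at the Day 90 step and runs the AECOPD and culture analyses in parallel. A decision to adjust taken after an imbalance has been seen would be data-driven.

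**Working it through.** **The plan's own figure.** Protocol Section 11.4 gives only AE-detection probabilities for 70 per group. 1 − 0.99^70 = 50.5% (stated: more than 50%) and 1 − 0.95^70 = 97.2% (stated: more than 97%). Both reproduce. No precision or power is stated for VE.

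**Inputs.** From the documents: 70 per group, 1:1, three minimisation factors. Assumed, because the documents give no value: carriage prevalence p (20% to 40%, central 30%), rate ratio r of carriers to non-carriers for the endpoint (1 to 5), and a true VE of 30% for illustration. Minimisation on the three factors is assumed to leave carriage unbalanced.

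**Step 1: size of a chance imbalance.** The SD of the between-group difference is √(2p(1−p)/70).
- p = 20%: 6.8 points
- p = 30%: √(2 × 0.3 × 0.7/70) = 0.0775, or 7.7 points
- p = 40%: 8.3 points

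The exact binomial chance of a difference of 10 points or more is 17%, 23% and 26%.

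**Step 2: effect on the unadjusted VE.** Spurious rate ratio = (1 + (r−1)p_V)/(1 + (r−1)p_C). Apparent VE = 1 − 0.70 × spurious ratio. For a 1-SD imbalance around 30%, the two prevalences are 33.9% and 26.1%.

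| Carrier rate ratio r | Spurious ratio | Its log | VE seen, more carriers on vaccine | VE seen, fewer carriers on vaccine |
|---|---|---|---|---|
| 1 | 1.00 | 0 | 30% | 30% |
| 1.5 | 1.03 | 0.03 | 28% | 32% |
| 2 | 1.06 | 0.06 | 26% | 34% |
| 3 | 1.10 | 0.10 | 23% | 36% |
| 5 | 1.15 | 0.14 | 19% | 39% |

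A 2-SD imbalance gives spurious ratios of 1.21 (r = 3) and 1.33 (r = 5), so 30% appears as 15% and 7% when the vaccine group has more carriers.

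**Step 3: compare with sampling error.** In simulation (1,500 trials, 70 per group, mean rate 0.25/year, dispersion 0.5, true VE 30%), the SD of the log rate ratio without and with the carriage term was:
- r = 3: 0.442 and 0.431, a reduction of 1 − 0.431/0.442 = 2.5%
- r = 5: 0.458 and 0.435, a reduction of 1 − 0.435/0.458 = 5%

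The 1-SD shift is 0.097/0.442 = 0.22 of a standard error at r = 3 and 0.141/0.458 = 0.31 at r = 5. With SD 0.442 and true VE 30%, the 95% range is 1 − 0.70 × exp(±1.96 × 0.442), or about −66% to +71%.

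**Step 4: does adjustment remove the dependence?** A second simulation used true VE 0, p = 30%, dispersion 0.8 and rates of 0.3 and 0.6/year.
- At r = 3 the slope of the log rate ratio on carriage imbalance fell from 1.25 and 1.42 to −0.04 and 0.14.
- The SD fell from 0.369 to 0.356 (3.5%) and from 0.308 to 0.286 (7%), so the precision gain depends on the assumed event rate.
- The mean log rate ratio was near zero with and without the term.
- At r = 1, adjustment changed almost nothing.

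**The case against.** The strongest reply is that chance imbalance is noise. Its expected effect under randomisation is zero, and the unadjusted 95% interval already covers it on average. That stands. What the interval does not do is hold its coverage conditionally on an imbalance that has been observed.

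The gain is also small. A re-run of the first simulation found the adjusted VE closer to the truth than the unadjusted VE in only 55% of trials at r = 3, 54% at r = 5, 52% at r = 2, 50% at r = 1.5 and 47% at r = 1. Adjustment moved the VE by more than 10 points in 19% (r = 3), 30% (r = 5), 7% (r = 2) and 3% (r = 1.5) of trials, but movement is not the same as improvement. This stands and limits the priority.

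The link itself is assumed. One sputum taken 14 to 28 days before Day 0, cultured by local routine methods, would have to predict events from Day 90 to Day 450. Turnover and misclassification would pull r towards 1. The case definition is provisional, and a new-strain definition would weaken the mechanism or remove it. This also stands.

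A reader might infer that the Screening result goes unused. The documents do not support that: Protocol Section 11.10 would display an imbalance by group, and SAP Sections 6.1.3 and 6.1.7.5 examine newly present H. influenzae. None of these corrects the VE, however. The newly-present analyses can also rest on visits after vaccination, where the vaccine may itself have changed carriage; Screening status cannot be affected in that way.

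**Conclusion.** The omission is real. The VE models for the two NTHi-associated endpoints contain no Screening H. influenzae term, and the allocation does not balance it. If Screening carriage predicts the endpoint, which is likely under the any-presence definition but not shown, a chance imbalance moves the estimate. At 30% carriage and 70 per group, a 1-SD imbalance moves a true VE of 30% by about 2 to 11 points for rate ratios of 1.5 to 5, in either direction, and by nothing at rate ratio 1. Prevalence, rate ratio and event rate are all assumptions.

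A reader might go further and infer that the planned VE is biased or its interval invalid. The documents and the arithmetic do not support that. The error has mean zero, is smaller than the standard error, and adjusting for it narrows the interval by only about 2.5% to 5% at rate ratios of 3 to 5 under the first simulation's assumptions.

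Priority is modest. Protocol Section 11.13 makes efficacy comparisons descriptive, and the sample size rests on AE detection. The case for acting is that the covariate is already planned, the SAP takes the same approach for antibodies, and the choice is credible only if made in advance.

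**What to change.** In SAP Section 6.1.3:
- Pre-specify Screening sputum H. influenzae status by culture (positive / negative / not available) as a covariate in the models for NTHi-associated moderate and severe AECOPD and NTHi-associated AECOPD of any severity.
- Report the model without this term alongside.
- If events are too few for the adjusted model to converge, make it the named sensitivity analysis instead.

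In SAP Section 6.1, show Screening status by group with the baseline characteristics.

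The cost is a few lines of SAP text on data already planned. The downside is one or two extra parameters when NTHi events may be few, including a level for subjects without a Screening sputum result.
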